### **7.2.7 Pre-dose Serological Markers - PGD2**

A single predose blood sample for circulating PGD2/PGD2 metabolites will be obtained at the time specified in [Table 1](#). Sample collection, handling, storage and shipment instructions will be provided in the study laboratory manual.

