### **8.7.2.1 Statistical Analysis of Pharmacodynamic Parameters**

## **8.8 Safety Analyses**

Safety endpoint:

1. Incidence and severity of treatment-emergent AEs (TEAEs)
2. Safety outcome measure:
  - a) Occurrence of AEs
  - b) Laboratory safety parameters such as complete blood count, blood glucose, electrolyte, hepatic and renal functions taken before the first dose and on Days 2, 5, 14, 28 and at the time of discharge to find any changes or any systemic effect after treatment

Adverse events will be coded using the Medical Dictionary for Regulatory Activities (MedDRA) Version 23.1. The number of events, incidence, and percentage of TEAEs will be calculated overall, by system organ class, by preferred term, and by treatment group for each cohort and treatment group. The number and percentage of subjects with TEAEs will be further summarized

by severity and relationship to IP. Adverse events related to IP, AEs leading to withdrawal, SAEs, and deaths will be similarly summarized/listed.

Clinical laboratory tests, vital signs, and ECG findings will be summarized by treatment group and visit for the study. Descriptive statistics will be calculated for quantitative safety data as well as for the difference from baseline, if applicable. Frequency counts will be compiled for classification of qualitative safety data. Baseline for safety data will be defined as the last value prior to dose. Potentially clinically important findings will also be summarized or listed.

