7. Time to clinical improvement from baseline value (defined by time to ≥ 1 -point improvement on WHO Ordinal Scale for COVID-19 score – must be maintained through Day 28)
8. Mean change from baseline in WHO Ordinal Scale for COVID-19 score at Day 14/End of Treatment, Day 28, Day 57
9. Incidence and duration of intubation
10. Length of intensive care unit stay (ICU)
11. Incidence and duration of supplemental O₂ administration
12. Incidence and duration of noninvasive ventilation or high-flow nasal cannula O₂ administration

13. Incidence and duration of mechanical ventilation
14. Incidence and duration of mechanical ventilation plus additional organ support using vasopressors, and/or renal replacement therapy and/or ECMO
15. Daily ratio of oxygen saturation (SpO_2) to fractional inspired O_2 ($\text{SpO}_2/\text{FiO}_2$)
16. Length of hospital stay
17. Incidence of re-hospitalization through Day 57
18. Proportion of patients requiring intensive care unit admission post randomization

Exploratory Endpoints

1. Inflammation markers including: IL-6, CRP, IL-10, TNF- α , IFN- γ , IFN- α , IP-10, MCP-1, and absolute lymphocyte count
2. Assess peak and trough concentrations of asapiprant at steady state
3. Assess PGD2 pre-diagnostic to assess correlation with response to treatment for COVID-19 based on change in the WHO Ordinal Scale for COVID-19 score

Safety endpoints

1. Incidence and severity of treatment-emergent AEs (TEAEs)
2. Safety outcome measure:
 - a. Occurrence of AEs
 - b. Laboratory safety parameters such as complete blood count, blood glucose, electrolyte, hepatic and renal functions taken before the first dose and on Days 2, 5, 14 and 28 and the time of discharge to find any changes or any systemic effect after treatment

3 Analysis Sets

Enrolled Analysis Set: all patients who provided informed consent.

Intent-to-Treat (ITT): all patients who have been randomized. The ITT will be used for efficacy endpoints. Patients will be analyzed according to the treatment group to which they were randomized. The ITT will be used for the primary efficacy analysis.

Modified Intent-to-Treat population (mITT): all ITT patients with exclusion of randomized untreated patients and randomized ineligible patients.

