4.6 Study Days

Study day is defined as the number of days since first dose of IMP and, for a particular date, and is calculated as:

Study day = Assessment date – Date of first dose of IMP + 1, if date of assessment is on or after date of first dose of IMP

or

Study day = Assessment date – Date of first dose of IMP, if date of assessment is prior to the date of first dose of IMP

Therefore, the date of the first dose of IMP will be Day 1.

In the situation where the assessment date is partial or missing, Study Day, and any corresponding durations will appear partial or missing in the listings.

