4.7 Definition of Baseline Values

The baseline value is defined to be the last non-missing assessment prior to randomization. For baseline WHO ordinal scale, if not collected prior to randomization, the earliest collected WHO ordinal scale collected on the same day as randomization will be used as baseline. Pre-randomization assessments on the same day as randomization will be considered the baseline assessment for each of these respective study procedures. Unless otherwise specified, change from baseline calculations for a treatment window assessment will be the applicable treatment window assessment minus the

baseline assessment. If either the treatment window assessment value or the baseline value is/are missing, then change from baseline will be set to missing.

Age in years will be calculated as (date of informed consent – January 01 of year of birth) / 365.2425.

4.8 *Planned Analyses*

The following statistical analyses are planned for this study:

- Unblinded safety analyses for Data Monitoring Committee (DMC): An independent DMC will be utilized throughout the study to monitor patient safety. DMC meetings for safety will be conducted after 33, 100, and approximately 208 subjects complete assessments through the 28-day follow up (Day 28), approximately 14 days after the final dose of study drug. A DMC charter will be developed preceding study initiation and will define DMC processes and meetings, and required report contents.
- Interim analysis: An interim look for safety and primary endpoint will be conducted by the DMC when approximately 208 patients in the ITT population complete assessments through the 28-day follow up (Day 28), approximately 14 days after the final dose of study drug.

When all subjects enrolled under the targeted or adjusted sample size have completed the study through Day 28 (i.e., full study enrolment is completed), the clinical database will be cleaned, frozen, and an assessment of the primary efficacy endpoint and secondary, exploratory, and safety endpoints up to Day 28 in the ITT population will be created. Individuals involved with the conduct of the study will not have access to unblinded data until database lock. Final analysis: final analysis on efficacy and safety will occur after the database is locked.

4.9 *Multiple Comparison/Multiplicity*

No multiplicity adjustment is planned.

5 Study Population and Disposition

5.1 *Analysis Population*

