10.2.1 Proportion of binary endpoints

The number and percentage of the following binary endpoints will be presented by treatment and timepoint. Comparison of proportion of patients between treatment at each timepoint will be analysed by the same manner as primary endpoint.

- Proportion of patients who had survived at each timepoint at Day 14, at Day 28, at Day 57: which is defined as patients who had no documented death prior or on timepoint at Day 14, 28, 57.
- Proportion of patients who survive without progression to RF at each timepoint at Day 14, Day 28, Day 57: which is defined as patients who had neither documented death nor respiratory failure prior or on timepoint at Day 14, 28, 57.
- Proportion of patients who had intubation during the study: which will be defined as proportion of patients who had any documented intubation during the study.
- Proportion of patients who develop critical COVID-19 illness as defined by at least one the following:
 - A. Respiratory failure defined based on resource utilization requiring at least one of the following: Endotracheal intubation and mechanical ventilation, oxygen delivered by high-flow nasal cannula (heated, humidified, oxygen delivered via reinforced nasal cannula at flow rates > 20 L/min with fraction of delivered oxygen ≥ 0.5), noninvasive positive pressure ventilation, ECMO clinical diagnosis respiratory failure (i.e., clinical need for one of the preceding therapies, but preceding therapies not able to be administered in setting of resource limitation)
 - B. Hemodynamic compromise (defined by systolic blood pressure < 90 mm Hg, or diastolic blood pressure < 60 mm Hg or requiring vasopressors)
 - C. Multi-organ dysfunction/failure
- Proportion of patients requiring intensive care unit admission: which is defined as patients who had been admitted to intensive care unit during the study.
- Incidence of supplemental O₂ administration: which will be defined as proportion of patients who had any documented post-dosing supplemental O₂ administration during the study.
- Incidence of noninvasive ventilation or high-flow nasal cannula O₂ administration: which will be defined as proportion of patients who had any documented post-dosing noninvasive ventilation or high-flow nasal cannula O₂ administration.
- Incidence of mechanical ventilation: which will be defined as proportion of patients who had any documented post-dosing mechanical ventilation.

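### Several secondary ITT endpoints in the SAP count only post-dosing events, and the SAP baseline rule conflicts with the protocol's pre-dose safety baseline (minor)

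*SAP*

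**What the plan says.** SAP section 3 defines ITT as "all patients who have been randomized. The ITT will be used for efficacy endpoints". The mITT definition in the same section removes randomized subjects who were not treated, so the plan expects that some may exist. SAP 10.2 analyses all secondary efficacy endpoints in ITT, mITT and (if formed) PPS, as randomized.

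Within SAP 10.2.1 the event definitions differ. Incidence of mechanical ventilation is an endpoint "which will be defined as proportion of patients who had any documented post-dosing mechanical ventilation", whereas intubation is counted if there was "any documented intubation during the study". In SAP 10.2.2 the time-to-event clocks start at randomization, but the qualifying assessment must be post-dosing. In SAP 10.2.4 most durations refer to the first post-dosing episode. SAP 4.6 adds: "Study day is defined as the number of days since first dose of IMP".

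On baseline, SAP 4.7 says: "The baseline value is defined to be the last non-missing assessment prior to randomization". A same-day exception is made for the WHO scale only, and a missing baseline makes the change from baseline missing. Protocol 8.8 says: "Baseline for safety data will be defined as the last value prior to dose". SAP section 1 states that the SAP prevails where the two differ. Protocol 7.2.7 ties the PGD2 measurement to dosing, as "A single predose blood sample for circulating PGD2/PGD2 metabolites".

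**The concern.** An ITT analysis keeps every randomized subject in the denominator. If an event counts only after a first dose, a subject who never receives one cannot have an event, whatever happens. An untreated subject who is ventilated would then be reported as not ventilated. Events between randomization and first dose are lost in the same way for subjects who are dosed later. At stake are the accuracy of several supportive endpoints and their consistency with the primary endpoint, which has no dosing condition.

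The baseline rule raises the reverse problem. By anchoring at randomization instead of dose, the SAP can reject a valid pre-treatment measurement that the protocol would accept. This matters most for a variable with no screening value to fall back on.

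**Working it through.** **Step 1. Which endpoints carry the condition.**

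| SAP section | Post-dosing condition | No dosing condition |
|---|---|---|
| 10.1 | none | Primary endpoint; time to death or RF |
| 10.2.1 | Incidence of supplemental O2; NIV or high flow; mechanical ventilation; ventilation plus organ support | Survival; RF-free survival; intubation; critical illness; ICU admission; re-hospitalization |
| 10.2.2 | Time to viral clearance; to worsening; to improvement | none |
| 10.2.4 | Durations of intubation, ICU stay, O2, NIV or high flow, ventilation, ventilation plus organ support | Length of hospital stay; daily SpO2/FiO2 |

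**Step 2. Follow one subject** who is randomized, never dosed, then intubated and ventilated.
- Primary endpoint and RF-free survival: counted as a failure.
- Incidence of intubation: counted.
- Incidence of mechanical ventilation: not counted, although it is the same clinical event.
- Duration of intubation: no qualifying episode, although the subject counts as intubated.
- Time to worsening: the WHO score of 6 is not post-dosing, so the subject is censored at Day 57 or at discontinuation.
- Study day: the SAP 4.6 formula needs a first-dose date and has no value here, so the Day 28 and Day 57 cut-offs are undefined.

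The rule in SAP 7.1 that sets a missing first-intake date to the randomization date does not help. It belongs to the exposure summary, which covers treated subjects only.

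**Step 3. Size of the efficacy effect.** The planned N supplies the denominator, so it is checked first. With 31% versus 15%, two-sided 5% and 90% power, the normal approximation with continuity correction gives 156 per arm = 312, as stated. Exact enumeration of Fisher's test at 156 per arm gives power 0.905. No stated figure is wrong on this point.

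The documents give no untreated share u and no event rates p for the affected endpoints. The following is therefore an illustration, not an estimate. It assumes u = 1 to 5%, borrows the RF design rates (31%, 15%) as stand-ins, and gives untreated subjects their arm's rate.

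Counted incidence = p(1 − u). Lost events per arm = 156 × u × p.

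| u | Lost, placebo | Lost, active | Difference, both arms at u | Only active untreated | Only placebo untreated |
|---|---|---|---|---|---|
| 1% | 0.48 | 0.23 | 15.84 | 16.15 | 15.69 |
| 3% | 1.45 | 0.70 | 15.52 | 16.45 | 15.07 |
| 5% | 2.42 | 1.17 | 15.20 | 16.75 | 14.45 |

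Differences are in percentage points, against 16.00 with no untreated subjects. Example: 0.31 × 0.95 − 0.15 × 0.95 = 0.2945 − 0.1425 = 0.1520. With untreated subjects in one arm only: 0.31 − 0.1425 = 0.1675, or 0.2945 − 0.15 = 0.1445.

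In the extreme case that every untreated subject had the event, the loss equals the number untreated: 156 × 0.01, 0.03 and 0.05 = 1.56, 4.68 and 7.8 per arm. The event counts rest on the planned 156 per arm. The SAP addendum says enrollment stopped before the interim analysis and does not give the number enrolled.

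**Step 4. Baseline.** In protocol Table 1 the ECG is on Day 1, Day 2, Day 14/EOT and at discharge, with none at screening. Its order relative to randomization on Day 1 is not stated. Protocol 6.2.2 has the first dose follow randomization immediately.

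| Day 1 ECG taken | Baseline under protocol 8.8 | Baseline under SAP 4.7 |
|---|---|---|
| Before randomization | yes | yes |
| After randomization, before dose | yes | no; change is missing |
| After dose | no | no |

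Only the middle row is a conflict. Laboratory tests and vital signs have screening values, so they are less exposed. PGD2 is a single sample with no change from baseline. The SAP 4.7 rule reaches it only through the PGD2 row among the baseline characteristics in SAP 6.1. Its timing is also inconsistent: the synopsis study design, protocol 3.1 and SAP section 2 list it under screening, while Table 1 has it on Day 1 only.

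**The case against.** The best defence is that little is at risk. Dosing follows randomization at once and should leave few untreated subjects. The affected endpoints are not key and carry no multiplicity claim, and SAP 10.2 also requires an mITT analysis with no untreated subjects. Most of this stands and sets the severity. The mITT analysis is not a full answer, though. It also drops ineligible subjects, and it still loses events between randomization and first dose.

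A reader might infer more than the text supports:
- *That all ITT efficacy events need a dose.* They do not; the right-hand column of the first table has no dosing condition.
- *That deaths disappear from the incidence endpoints.* Death is not an event in the oxygen or ventilation endpoints under any anchor, and survival counts it without a dosing condition. A pre-dose or undosed death is missed only in time to worsening.
- *That one arm is favoured.* Assignment is blinded, and deterioration before any dose cannot be a drug effect, so a shift towards either arm needs an imbalance in who goes undosed. The rule also hides favourable events (improvement, viral clearance).
- *That no visit can be mapped for an undosed subject.* SAP 4.5 maps visits by name, and the clocks in SAP 10.1 and 10.2.2 start at randomization. The study day is undefined, but the visit is not necessarily lost.
- *That the PGD2 correlation loses subjects.* No text restricts that correlation to a PGD2 value meeting SAP 4.7, and the WHO score it uses has its own baseline exception.

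**Conclusion.** The point holds for the named endpoints in SAP 10.2.1, 10.2.2 and 10.2.4. As written, their event definitions do not match the ITT set in which they are analysed, and they conflict with the intubation definition in the same list. The event definitions of the primary endpoint and the other endpoints without a dosing condition are not affected. The only residual issue for those is the undefined study day for an undosed subject.

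The size cannot be derived from the documents. Under the assumptions above it is about 2 to 3 events or fewer per arm. The shift is under 1 point with equal untreated shares, and between −1.55 and +0.75 points if all untreated subjects fall in one arm. It would be larger only if deterioration was itself the reason for not dosing.

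The baseline conflict is also real. Its practical reach is the descriptive ECG change summaries and one descriptive PGD2 row. Loss occurs only if the measurement falls in the short gap between randomization and dose, and the documents give no frequency for that. Severity: minor.

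**What to change.** - In SAP 10.2.1, 10.2.2 and 10.2.4, replace the post-dosing condition with a post-randomization condition for the endpoints in the middle column of the first table.
- In SAP 4.6, count efficacy study days from randomization, with the randomization date as Day 1. Safety may keep the first-dose anchor.
- In SAP 4.7, define the safety and ECG baseline as the last value before first dose, as protocol 8.8 does.
- For PGD2, use the single pre-dose sample as the baseline value, and reconcile the screening and Day 1 descriptions of its timing.

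The cost is SAP wording and a few programming lines, best settled before unblinding. No site procedure changes. Table 1 places randomization and first dose on the same day, so almost nothing should change for dosed subjects.

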10.2.2 Time to event endpoints

Following time to event endpoints will be presented by treatment group, using the Kaplan-Meier estimator. A Cox proportional hazards model with treatment, previous COVID-19 therapy (yes/no), region, and age group (50 to < 75 vs. ≥ 75 years of age) as covariates will be used to estimate the hazard ratio and compare treatment groups. In addition, the log rank test and stratified log rank test, with age group and region as the strata, will be provided.

- Time to two successive negative viral titers in nasopharyngeal swab: which is defined as time from the date of randomization to the date of second post-dosing viral titers collection with negative result of two successive negative viral titers tests. If a patient doesn't have documented two successive negative viral titers, it will be censored at the date of Day 28 or date of discontinuation from study, which ever comes earlier.
- Time to clinical worsening from baseline value (defined by time to ≥ 1 -point worsening on WHO Ordinal Scale for COVID-19): which is defined as time from the date of randomization to the date of first post-dosing collection of WHO Ordinal Scale for COVID-19 showing higher than baseline, i.e., ≥ 1 -point worsening. If a patient doesn't have documented worsening post-baseline WHO Ordinal Scale, it will be censored at the date of Day 57 or date of discontinuation from study, which ever comes earlier.
- Time to clinical improvement from baseline value (defined by time to ≥ 1 -point improvement on WHO Ordinal Scale for COVID-19 score – must be maintained through Day 28): which is defined as time from the date of randomization to the date of first post-dosing collection of WHO Ordinal Scale for COVID-19 showing a decrease from baseline, i.e., ≥ 1 -point decrease demonstrating clinical improvement. If a patient doesn't have documented improving post-baseline WHO Ordinal Scale, it will be censored at the date of Day 28 (including death prior to Day 28) or date of discontinuation from study, whichever comes earlier.

10.2.3 Mean change in WHO Ordinal Scale for COVID-19 score at Day 14/End of Treatment, Day 28, Day 57

Mean change in WHO Ordinal Scale at Day 14, 28, and 57 will be analyzed using ANCOVA on change at each time point. The model will include the stratification factors. The least squares means (LS-means) for each treatment, LS-means treatment difference and corresponding CI for the LS-means difference and p-value for the treatment difference, will be reported at the Day 14, 28, and 57.

Results from Wilcoxon rank sum test and t-tests will also be reported for change in WHO Ordinal Scale at the Day 14, 28, and 57.

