10.2.4 Other continuous secondary efficacy endpoints

Following continuous endpoints will be analyzed using an analysis of covariance (ANCOVA) model, with treatment as a fixed effect and baseline WHO Ordinal Scale score, age group (50 to < 75 vs. ≥ 75 years of age) and region. Results from Wilcoxon rank sum test and t-tests will also be reported. The ITT and PP analysis (if formed) sets will be used for these exploratory subset analyses.

- Duration of intubation: which will be defined as duration of first post-dosing intubation based on start and end date of the intubation.

QMS Document Name: Statistical Analysis Plan	Page 21 of 27
QMS No (include version ref): STF-015-GL.02	Document date: 09JUL2019
CONFIDENTIAL	

- Length of intensive care unit (ICU) stay in days which will be defined as duration of first post-dosing ICU stay based on start and end date/time of the stay.
- Duration of supplemental O₂ administration in days : which will be defined as duration of first post-dosing supplemental O₂ administration based on start and end date/ of the O₂ administration.
- Duration of noninvasive ventilation or high-flow oxygen therapy in days: which will be defined as duration of first post-dosing noninvasive ventilation or high-flow oxygen therapy based on start and end date/time of the noninvasive ventilation or high-flow oxygen therapy.
- Duration of mechanical ventilation in days: which will be defined as duration of first post-dosing mechanical ventilation based on start and end date/time of the mechanical ventilation.
- Duration of mechanical ventilation plus additional organ support using vasopressors, and/or renal replacement therapy and/or ECMO: which will be defined as duration of first post-dosing mechanical ventilation plus additional organ support using vasopressors, and/or renal replacement therapy and/or ECMO based on start and end date/time of the mechanical ventilation plus additional organ support using vasopressors, and/or renal replacement therapy and/or ECMO.
- Daily ratio of oxygen saturation (SpO₂) to fractional inspired O₂ (SpO₂/FiO₂): which will be defined as SpO₂/FiO₂ as collected in CRF. The ratio will be analyzed for each day with the value being collected. If FiO₂ was not collected for some O₂ delivery methods, following guide can be followed to convert O₂ flow rate to FiO₂.

O ₂ delivery method	O ₂ flow rate (l/min)	Estimated FiO ₂
Nasal cannula ("NASAL CANNULA LARGE TUBING" and "NASAL CANNULA TRADITIONAL TUBING")	1	24
	2	28

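### SAP 10.2.2 omits baseline WHO score from the worsening and improvement analyses and baseline titer from the clearance model, which costs efficiency but not validity

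*SAP*

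**What the plan says.** SAP 10.2.2 uses one specification for all three endpoints: "A Cox proportional hazards model with treatment, previous COVID-19 therapy (yes/no), region, and age group". It adds that "the log rank test and stratified log rank test, with age group and region as the strata, will be provided". Protocol 8.4 names Kaplan-Meier, log-rank and Cox methods for time-to-event endpoints and lists no covariates, so it does not supply a baseline term.

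The events are defined as follows in SAP 10.2.2:

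- Worsening is the "first post-dosing collection of WHO Ordinal Scale for COVID-19 showing higher than baseline". Without an event, "it will be censored at the date of Day 57 or date of discontinuation from study".
- Improvement is the "first post-dosing collection of WHO Ordinal Scale for COVID-19 showing a decrease from baseline", with censoring at Day 28.
- Clearance is dated at the "second post-dosing viral titers collection with negative result of two successive negative viral titers tests", also with censoring at Day 28.

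Elsewhere, SAP 10.2.4 analyses the other continuous secondary endpoints "with treatment as a fixed effect and baseline WHO Ordinal Scale score", together with age group and region. The SAP Addendum (section 16) removes baseline WHO score from the primary logistic regression only. Its reason is that blinded review found no respiratory failure among subjects who started at score 3.

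**The concern.** Two of the three events are counted from the subject's own baseline WHO score, so the step that triggers an event depends on where the subject began. On the scale in Protocol Table 2, worsening from 3 means starting oxygen by mask or prongs, while worsening from 4 means high-flow oxygen, ventilation or death. Improvement from 3 means reaching an ambulatory state, while from 4 it means coming off oxygen. These steps are unlikely to occur at the same rate, yet neither the Cox model nor the log-rank strata separate the two groups.

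Clearance is the only listed endpoint that directly measures the first secondary objective, faster viral clearance. A subject with a higher starting titer plausibly takes longer to turn negative in either arm.

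Leaving out a prognostic baseline value from a proportional hazards model pulls the estimated hazard ratio toward 1, lowers power, and leaves chance imbalance between arms uncorrected. The data needed to avoid this are already scheduled.

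**Working it through.** **1. Does a stated reason cover the omission?** The Addendum's reason is quasi-complete separation on respiratory failure in the primary logistic model. In SAP 10.2.2 a move from 3 to 4 counts as worsening, and a subject at 3 can also improve, so separation on respiratory failure does not carry over automatically. A stratum also needs no coefficient for the score. SAP 10.2.4 keeps the score. No reason is given for leaving it out of 10.2.2.

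**2. The plan's only sizing figure.** SAP 2.2 assumes 31% vs 15%, two-sided 5% and 90% power. The mean rate is 0.23.

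- n per arm = [1.96·√(2·0.23·0.77) + 1.2816·√(0.31·0.69 + 0.15·0.85)]² / 0.16² = (1.166 + 0.749)² / 0.0256 ≈ 143.3, so 144 per arm (288 in total).
- With continuity correction: (143.3/4)·[1 + √(1 + 4/(143.3·0.16))]² ≈ 155.5, so 156 per arm, or **312**. Exact Fisher power at 156 per arm is 90.5%.

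The stated 312 reproduces. The documents give no power, hazard ratio or event count for the time-to-event endpoints, so the rest is illustrative.

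**3. Simulation.** Inputs: 312 subjects, 1:1, exponential times with hazard λ₀·exp(ln HR·treatment + ln γ·baseline), 28 days of follow-up for every endpoint, |Z| > 1.96. Each data set was analysed without and with the baseline term, with 2,500 runs (Cox covariate) or 4,000 runs (stratified). Age, region and prior therapy were left out of both analyses. HR, γ, the event rates and the share at score 3 are all assumptions. At 80% power the Monte Carlo error of one figure is about √(0.8·0.2/4000) = 0.6 points.

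| Endpoint, analysis and assumed baseline effect γ | HR without / with | Power % without / with | Gain (points) |
|---|---|---|---|
| Clearance, HR 1.4, Cox covariate, γ 1.3 per SD | 1.374 / 1.397 | 74.8 / 79.0 | 4 |
| same, γ 1.5 | 1.356 / 1.403 | 72.0 / 79.0 | 7 |
| same, γ 2.0 | 1.305 / 1.407 | 58.0 / 79.8 | 22 |
| same, γ 2.5 | 1.266 / 1.405 | 48.2 / 79.4 | 31 |
| Improvement, HR 1.4, 30% at score 3, stratified, γ 1 | 1.400 / 1.400 | 80.5 / 79.5 | none |
| same, Cox covariate, γ 1.5 | 1.396 / 1.409 | 81.2 / 83.2 | 2 |
| same, stratified, γ 2 | 1.370 / 1.398 | 74.9 / 80.1 | 5 |
| same, stratified, γ 3 | 1.344 / 1.402 | 68.4 / 79.2 | 11 |
| 10% at score 3, Cox covariate, γ 3 | 1.384 / 1.407 | 76.9 / 80.7 | 4 |
| Worsening, HR 0.55, stratified, 10% at score 3, γ 0.02 | 0.552 / 0.546 | 73.6 / 74.6 | 1 |
| same, 30% at score 3, γ 1 | 0.548 / 0.548 | 69.5 / 69.2 | none |
| same, 30%, γ 0.02, 19% events | 0.561 / 0.544 | 59.0 / 63.1 | 4 |
| same, 30%, γ 0.02, 33% events | 0.579 / 0.545 | 78.5 / 86.1 | 8 |

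For worsening with HR 0.5 and a Cox covariate, the gain was 0.3 to 2.1 points in all five scenarios tried.

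**4. Under no treatment effect.** Rejection was 4.6 to 5.2% with or without the baseline term.

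**5. Fewer subjects.** The Addendum says enrollment stopped before the interim analysis, which was planned at about 208 subjects, so 312 may not have been reached. With HR 1.45, 75% control events by Day 28 and titer hazard ratios of 0.74, 0.61 and 0.50 per SD (1,500 runs), power without vs with titer was 79 vs 83%, 73 vs 83% and 65 vs 82% at 312. At an assumed 200 it was 61 vs 65%, 53 vs 63% and 46 vs 65%.

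**The case against.** A reader might infer that the current analyses are invalid or raise the false-positive rate. They do not: the null check is at the nominal level, and a hazard ratio without the baseline term is a legitimate marginal quantity. SAP 10.2.2 already adjusts for both randomization factors and prior therapy. This stands, and it limits the point to efficiency.

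A reader might also infer that all three events are measured from a starting value. Clearance is not. It is an absolute threshold, so titer matters there only as a likely predictor, and the documents give no figure for its strength.

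The larger power losses depend on assumptions. The documents do not give the share at score 3. Entry requires room-air saturation of 94% or less, so it may be small. With HR 1.45 and 75% events, stratifying gained about 1 point at a 5% share and 1 to 3 points at 10%. The clearance simulation also treats time as continuous. Under Protocol 7.2.8 and Table 1, swabs are taken every other day, outpatients may skip some, and after local negatives only Day 28 is tested. The worsening simulation stops at Day 28, whereas the SAP follows to Day 57. All of this stands.

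The endpoints are secondary. Protocol 8.4 names none as key and corrects none for multiplicity, so the trial's main conclusion is not at stake.

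Finally, a baseline term does not remove the mixing of clinical steps, because a stratified model still reports one treatment hazard ratio across starts from 3 and from 4. That is correct. The stratum only ensures that subjects are compared with others who face the same step.

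None of this supplies a reason for omitting data already collected.

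**Conclusion.** The point holds as a modest efficiency gap. It is firmest for the two WHO endpoints: their events are defined from the baseline score, the Addendum shows the score predicts respiratory failure, and SAP 10.2.4 adjusts for it. It is weaker for titer, where prognostic strength is plausible but undocumented.

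In the simulations the loss was 0 to 2 power points where baseline was not or only modestly prognostic. It can be as small with few subjects at score 3. It was about 4 to 11 points for moderate to strong effects, and 22 to 31 only with a titer effect of 2.0 to 2.5 per SD. For worsening it ranged from nothing to about 8 points and may be negligible. These figures rest on assumed hazard ratios, event rates and score-3 shares at 312 subjects, and they are not estimates for this trial. The documents do not support reading the gap as an error in the tests, as a shortfall against any stated power, or as a threat to the primary result.

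**What to change.** Before unblinding, amend SAP 10.2.2:

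- **Worsening and improvement.** Stratify the Cox models by baseline WHO score (3 vs 4), and add that score to the strata of the stratified log-rank tests. Use a stratum and not a covariate: the Addendum does not say whether any score-3 subject worsened, and if none did, a coefficient would have no finite estimate. Adding the score doubles the log-rank strata from 4 to 8 (2×2×2), so also give a test stratified by WHO score alone if cells are sparse.
- **Clearance.** Add log10 baseline titer to the Cox model, taking the last value before randomization as SAP 4.7 defines baseline. Entry allows illness of any duration, so a baseline titer may be negative. Set negatives to a fixed value such as half the detection limit, and use a missing indicator where there is no baseline value.

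The cost is SAP wording, these handling rules and slightly sparser strata. No new data are needed.
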